5.6 Data Analysis

• Table 8. Seven Key Data Elements		Timing	Source
1. Veteran Characteristics			
Participant Demographics	1	S,C	
Comorbidities, VA Utilization	1	C	
2. Intervention Dose/Exposure			
Number of videos watched and time spent viewing	2	S	
Which was selected video?	2	S	
3. Narrative Communication			
Video Transportation Scale	2	S	
Homophily (personal relevance)	2	S	
4. Social Cognitive Theory			
Beliefs About Medications (BMQ)	1,4	S	
Self-efficacy for hypertension (e.g.: MASES-R, PEPP)	1,4	S	
5. HTN management behaviors			
Avoid Salt, Be Physically Active, Monitor your BP (H-SCALE, PEMH)	1,4	S	
Talk with your doctor (H-SCALE)	1,4	S	
Take Your Medicines: Morisky ; and administrative data adherence (MPR)	1,3,4	S, C	
6. Primary Outcome (H1)			
Measured BP (systolic/diastolic)	1,4	BP, C	
7. Implementation Data/Process Measures/Fidelity			
Text message opening (subgroup)	3	T	
Responses to text assessment	3	T	
Confirmation of text receipt	4	S	
Phone calls for texting assistance	3	RA	
Staff time spent for implementation	3	RA	
Persistence/Early Discontinuation of Texting Protocol	3	T	
Reasons for discontinuation	5	P	

1=Baseline, 2=Immediately post-Video Viewing; P, 3=Repeated throughout 6-month study period, 4 = six-month follow-up; 5= phone call to drop-out

Source: S = Survey; C = CDW data; RA=Research assistant; T=Texting System;

P=phone call to participant; BP = Blood pressure cuff, standard protocol (For BP measurement at 6-months, we will pull CDW data for the entire study participation period)

With our recruited sample of 600 (and assuming follow-up rates, over-time within-person correlation, and BP standard deviations from our prior work (85% follow-up, correlation = 0.5, SD = 18 (equivalent to variance of 324)), we have over 80% power (alpha 0.05) to detect a difference of 5mm Hg. In fact, we calculated power for a range of scenarios, and are able to maintain the 5mm Hg detection with a lower follow-up rate of 82%.

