Missingness not at random may introduce bias. Advance planning through sound data collection and quality control will be used to minimize this bias. We will use all available data regardless of whether a patient has a complete record. Group means will be reported as least-squares means, the predicted marginal mean values, or those that would be expected with a balanced design. Participants with missing data will be compared to those without. Inverse probability weight in and pattern-mixture modeling using the longitudinal data structure, for non-ignorable missing data, will be considered.

Covariates for Adjustment Models

We will look at the balance of randomization and adjust for demographics and behavioral variables if imbalanced.

Data Transformations

N/A

Analytical Sets

We intend to include all patients in intent to treat analysis.

Monitoring Adverse and Serious Events

Because this is a low-risk trial of an educational DVD, we do not expect SAE's or AE's. We will plan to report any SAE's defined as death of participant or hospitalizations reported at 6-month follow-up.

At the time of recruitment, patients experiencing hypertensive urgency, as defined by JNC as Blood Pressure Systolic \geq 180 OR Diastolic \geq 120, regardless of symptoms, will be referred to urgent care and a notification letter will be sent to their primary care physician. If a patient reports symptoms related to the hypertensive urgency, even if before viewing the intervention DVDs, this will also be reported as an AE. AE's also include stress related to watching the DVD. All AE's reported at baseline and 6-month follow-up will be recorded and submitted at Continuing Review.

Analysis Plan

We will first identify key distributional features for all variables of interest (non-normality, skewness, ceiling or floor effects, presence of implausible values, outliers, etc.) and calculate descriptive statistics. We will document recruitment and retention with a CONSORT diagram. Following best practice, baseline differences between intervention and comparison groups will be based on standardized differences, not simply tests of statistical significance. All primary hypotheses will be tested by intent-to-treat; secondary analyses will account for important covariate imbalances between groups, levels of adherence to the intervention protocol, and missing data. All analyses will be two-sided, with alpha error = 0.05.

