Hypothesis 1: (Primary Hypothesis) The difference in blood pressure from baseline to 6 months will favor CTC intervention group by 5mm Hg, compared with the change in control.

H1 postulates a difference-in-differences between study groups. We will use study group, assessment time, and group-time interactions as predictors in regression models. With this parameterization, the coefficient for the group-time interaction represents differential change for intervention vs. comparison. Multilevel mixed-effects generalized linear models will: (1) model the outcome distribution with an appropriate link function; (2) account for clustering of repeated measures within individual; (3) adjust for observed group imbalances as secondary analyses; and (4) support secondary mediation analyses as described below. The most general structure of the mixed model is $y = X\beta + Z\gamma + \epsilon$, where the y matrix is the observed outcomes, β is a vector of fixed-effect parameters with design matrix X , γ is a vector of random-effect parameters with design matrix Z , and ϵ is a random-error vector. We will assume that γ is independent of ϵ and has a multivariable normal distribution with mean $\mathbf{0}$. We will examine residuals to seek gross violations of underlying assumptions, and explore approaches to address violations such as variable transformation, outlier trimming, or placing bounds on the extent that extreme observations can affect conclusions.

Hypothesis 2: Self-efficacy and hypertension management behaviors during 6-month follow-up will be greater for those in the CTC intervention group than comparison.

As Self-efficacy and HTN management behaviors (salt intake, physical activity, doctor-patient interaction, monitor BP) will be measured as self-report at baseline and follow-up, we can measure these as differences in change ("difference-in difference") between study groups, and mirror the analysis plan for H1.

In addition to self-report, for "Take your medicines" (medication adherence) we will use administrative data to calculate refill-based measures (ie: MPR) for each HTN medication and average these over six-month periods (before and during intervention). We will again use a repeated measures analysis (like H1).

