Secondary Analyses: Covariates to account for substantial imbalances in group characteristics will be added to our main regression models. Secondary analysis will occur for the separate measures of HTN management behaviors and BP change. As in our prior trials, we will also conduct secondary stratified analyses above and below the median mean arterial pressure at baseline (in our prior VA stories, we found the effect greater in those below the median baseline BP (see Section B5.b)). We will also analyze effect by site, by chosen storyteller and by age group. Further, using the administrative data for MPR, we have a pragmatic opportunity to study sustainment of effect after the six-month CTC is completed. For the subset of patients with six-months completed before Year 4, we will also calculate MPR six months after the end of CTC. In a secondary model, three time periods (before, during, after CTC) will be jointly tested using "segmented regression" to account for the three time periods.

Hypothesis 3: The effect of CTC on BP will be mediated by the more proximal measures of (H3a) cognitive and emotional processes (i.e.: emotional engagement with stories, self-efficacy), and (H3b) HTN management behaviors.

For this hypothesis, we will conduct a formal mediation analysis. Initial methods will follow Barron and Kenny's

protocols, with more recent advances developed by MacKinnon. Mediation occurs when an intervention changes the rate of uptake of an intermediate process that directly influences outcome. Mediation analysis can help to disentangle the mechanisms which may contribute to intervention effectiveness. We will estimate the proportion of the intervention effect that is transmitted through each of these mediators and quantify the precision of these estimates with 95% bias-corrected and accelerated bootstrap confidence intervals. Thus, we will be able to quantify the relative proportional mediation for each of the measures listed in Hypothesis 2.

Power Calculations

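### The mediation analysis (H3) names no baseline covariates and no model form, so a behaviour with no effect on BP can be reported as a mediator

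*SAP*

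**What the plan says.** SAP, Analysis Plan, Hypothesis 3, gives the method as "Initial methods will follow Barron and Kenny's" "protocols, with more recent advances developed by MacKinnon". The target is a proportion for each mediator: "We will estimate the proportion of the intervention effect that is transmitted through each of these mediators". Precision comes from "95% bias-corrected and accelerated bootstrap confidence intervals". The Hypothesis 1 text says that the mixed models will also "4) support secondary mediation analyses as described below". It does not say whether the mediator enters as a 6-month value, a change score or a time-varying covariate.

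The covariate rules are elsewhere in the SAP, and all are triggered by comparing arms. Covariates for Adjustment Models says the team will "adjust for demographics and behavioral variables if imbalanced". The Hypothesis 1 model adjusts for observed group imbalances as a secondary analysis. Secondary Analyses says: "Covariates to account for substantial imbalances in group characteristics will be added to our main regression models".

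Table 8 (Protocol 5.6 and SAP, Data Collection) schedules demographics, comorbidities and BP at baseline, along with most of the mediators, for example "Self-efficacy for hypertension (e.g.: MASES-R, PEPP"). The narrative scales are taken only immediately after video viewing.

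**The concern.** Only the arm is randomised. Self-efficacy, salt intake, activity and adherence are not. Age, comorbidity or long-standing adherence can drive both the behaviour and BP, and this happens inside perfectly balanced arms. A rule that adds covariates when the arms differ therefore does not select the variables that confound the mediator-to-BP path. Without them, the slope of BP on the mediator partly reflects who the Veteran already was, and the bootstrap interval is centred on that biased value.

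H3 is the trial's evidence on how narrative works, and the SAP intends to rank mediators by their share of the effect. Confounding can create a share where none exists and can change the ranking.

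**Working it through.** **Inputs from the SAP.** 600 recruited and 85% followed up give 600 × 0.85 = 510, or 255 per arm (1:1 is assumed; the ratio is not stated). BP SD is 18 mm Hg, within-person correlation 0.5, CTC effect 5 mm Hg, two-sided alpha 0.05.

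**Assumptions not in the documents.** The true mediator effect on BP is zero. One baseline factor correlates +g with the mediator and -g with BP. CTC shifts the mediator by 0.29 SD.

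**1. The plan's own H3 figure.** Power Calculations says 200 participants give 80% power with both paths at 0.29, which the SAP labels r.
- Arm to mediator: z = 0.29√200 / √(1 - 0.29²) = 4.29, power 0.990.
- Mediator to BP: z = 0.29√200 = 4.10, power 0.984.
- Both: 0.990 × 0.984 = 0.974.

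The claim is reproduced; simulation also gives 97%. The calculation contains no confounder.

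**2. False mediation on 6-month values, no covariates.** Mediation is declared when both paths are significant.
- Arm to mediator: z = 0.29√(255/2) = 3.27, power 0.906.
- Mediator to BP: the within-arm correlation is -g², so z = g²√510 / √(1 - g⁴) and the spurious slope is -18g² mm Hg per SD.
- Spurious indirect effect in size: 0.29 × 18 × g².

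| g | z, mediator to BP | Chance significant | False mediation (× 0.906) | Spurious indirect effect | Share of 5 mm Hg |
|---|---|---|---|---|---|
| 0.1 | 0.23 | 0.056 | 5% | 0.05 mm Hg | 1% |
| 0.2 | 0.90 | 0.148 | 13% | 0.21 mm Hg | 4% |
| 0.3 | 2.04 | 0.532 | 48% | 0.47 mm Hg | 9% |
| 0.4 | 3.66 | 0.955 | 87% | 0.84 mm Hg | 17% |

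Simulations agree: 48 to 50% at 0.3, 12 to 14% at 0.2 and about 5% at 0.1. If 0.29 is read as r, the shift is 2 × 0.29 / √(1 - 0.29²) = 0.61 SD. With 0.6 SD the formula gives 15% at g = 0.2 and 53% at 0.3, with a spurious share of 9% and 19%. Using 0.29 SD therefore does not inflate the result.

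**3. Dependence on the model form (simulated, g = 0.3, shift 0.29 SD).**

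| Analysis | False mediation |
|---|---|
| 6-month values, both paths significant | 48 to 50% |
| 6-month values, BCa interval as in the SAP | 58% |
| Random-intercept model, time-varying mediator, stable factor | 47% |
| Change on change, factor acts equally at both times | about 4% |
| Change on change, factor acts on 6-month values only | 45 to 47% |
| 6-month values adjusted for baseline mediator and BP, stable factor | 9 to 11% |
| The same, factor acts on 6-month values only | 73 to 76% |
| 6-month values adjusted for the factor itself, measured without error | about 5% (BCa 7 to 10%) |

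Subtracting baseline cancels a factor that contributes equally at both visits, which is why change scores do well in that one case. A random intercept does not cancel it, because between-person differences still inform the mediator slope.

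**The case against.** The SAP is silent on H3 covariates; it does not rule them out. Baron-Kenny is described as the initial method only, and the MacKinnon extensions could include covariates. The H2 measures are framed as differences in change, so change-on-change is a fair reading, and with a stable factor it shows no excess error. The correlations are assumed, and at 0.1 there is no problem. All of this stands, and it limits the size of the point. It does not close it: the MacKinnon reference and the BCa interval add no stated confounder control, and change scores fail when the factor drives change.

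Two stronger readings are tempting.
- A reader might infer that H3 stops if H1 is not significant, because the classical Baron-Kenny sequence starts from a significant total effect. The SAP states no such gate. It adds MacKinnon's methods, commits to bootstrap intervals for each mediator, and bases H3 power on the two mediation paths.
- A reader might take about 5% as the error rate to expect after adjustment. That figure needs the confounder itself, perfectly measured. Real covariates are proxies, and adjusting for baseline mediator and BP alone can leave about 10%, or do worse than no adjustment if the factor acts only later.

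**Conclusion.** The point holds as a gap in specification with a real consequence. As written, H3 does not address confounding between a non-randomised mediator and BP, and the imbalance rules do not fill that gap. If 6-month values are analysed, false mediation is about 49% at correlations of 0.3 and -0.3, 12 to 14% at 0.2, and nominal at 0.1. This rests on a true mediator effect of zero, a CTC shift of 0.29 SD, one shared factor acting in the direction that mimics mediation, and 510 analysed. A change-on-change model escapes only if the factor is stable over time. The residual error after adjusting for the recommended covariates cannot be computed from the documents. The SAP itself calls the mediation analyses secondary, and the H1 test is untouched.

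**What to change.** In SAP, Analysis Plan, Hypothesis 3:
- State how the mediator and BP enter the model (6-month value, change, or time-varying).
- Fit the mediator model and the BP model with the same pre-specified baseline set, whatever the balance between arms: baseline value of that mediator where one exists, baseline BP, age, sex, site, comorbidity and baseline MPR.
- State the assumption of no unmeasured mediator-BP confounding.
- Add a sensitivity analysis showing how large a residual mediator-BP correlation would remove the indirect effect.
- Treat emotional engagement separately. Table 8 measures the narrative scales only after video viewing, which Protocol 5.1 describes as an intervention-arm procedure, so there is no baseline value to adjust for.

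The cost is SAP wording and minor programming. The listed covariates are already known at randomisation or scheduled in Table 8, so no new data collection is needed. Fixing them before analysis also prevents selective adjustment across several mediators.

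### H3 is summarised only as a proportion mediated per measure; the indirect effect in mm Hg should be the main estimate, because the ratio is unstable if the blood pressure effect is small

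*SAP*

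**What the plan says.** The SAP's Analysis Plan, under Hypothesis 3, sets out a formal mediation analysis. On method it says "Initial methods will follow Barron and Kenny's" protocols, with later developments by MacKinnon. On the summary it says "We will estimate the proportion of the intervention effect that is transmitted through each of these mediators", and it will "quantify the precision of these estimates with 95% bias-corrected and accelerated bootstrap confidence intervals". From this it concludes that "we will be able to quantify the relative proportional mediation for each of the measures listed in Hypothesis 2".

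The measures come from Hypothesis 2: "Self-efficacy and HTN management behaviors (salt intake, physical activity, doctor-patient interaction, monitor BP) will be measured as self-report at baseline and follow-up". For medication adherence there is self-report, and in addition "we will use administrative data to calculate refill-based measures (ie: MPR) for each HTN medication".

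The plan does not:
- say whether each mediator has its own model or all enter one model;
- ask for an indirect effect in mm Hg;
- say what is reported if the total effect is small or its interval includes zero.

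Under Hypothesis 1 the SAP describes mediation as secondary.

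**The concern.** A proportion mediated is the indirect effect divided by the total effect. If the total effect is small relative to its standard error, the denominator can come close to zero or change sign, and the ratio can fall below 0 or exceed 1 even when the numerator is well estimated. A bootstrap interval displays that behaviour but does not remove it.

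The second issue is overlap. The Hypothesis 2 measures are likely to be correlated. Self-reported adherence and refill-based adherence describe one behaviour, and self-efficacy may act through the behaviours. If each is fitted alone, each share absorbs part of what belongs to the others, so the shares do not add up and their order has no clear meaning.

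At stake is whether H3 gets a usable answer about mechanism. The H3 power statement in the SAP concerns standardized mediation paths of 0.29 or larger. That relates to detecting an indirect effect, not to the precision of a ratio.

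**Working it through.** **Inputs from the SAP, Power Calculations:** 600 recruited, 85% follow-up, within-person correlation 0.5, SD 18 mm Hg, target difference 5 mm Hg, earlier effect as low as 2.7 mm Hg. Alpha is 0.05, two-sided (Analysis Plan). Allocation is not stated; 1:1 is assumed, giving 600 × 0.85 / 2 = 255 per arm.

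**1. Reproduce the plan's power.** SD of change = 18 × √(2 × (1 − 0.5)) = 18.0. With 255 per arm, power for 5 mm Hg is 88.0%. At 82% follow-up (246 per arm) it is 86.9%. Both agree with the SAP's claim of over 80%. The SAP gives no figure for any mediated proportion.

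**2. Precision of the denominator.** SE of the total effect = 18 × √(2/255) = 1.59 mm Hg.

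| True total effect | z | 95% CI includes 0 | Estimate has wrong sign |
|---|---|---|---|
| 5 mm Hg | 5/1.59 = 3.14 | 12% | 0.1% |
| 2.7 mm Hg | 2.7/1.59 = 1.69 | 60% | 4.5% |

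**3. Ratio against mm Hg.** Simulated trials with 255 per arm and SD of change 18. These assumptions are not in the documents: two mediators correlated 0.6, each shifted 0.3 SD, true joint share 40%, no mediator-outcome confounding. Both mediators are in one model. The true indirect effect is 0.40 × 5 = 2.0, or 0.40 × 2.7 = 1.08 mm Hg.

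| Total effect | 95% sampling range of the share | Share outside 0-100% | 95% sampling range of the joint indirect effect |
|---|---|---|---|
| 5 mm Hg | about 19% to 98% | about 2.5% | 0.9 to 3.2 mm Hg |
| 2.7 mm Hg | about −207% to 321% | about 16% | 0.4 to 2.0 mm Hg |

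The extreme percentiles at 2.7 mm Hg move between repeated runs of 4,000 trials (lower end −151% to −207%, upper end 254% to 321%). The fraction outside 0-100% stays at 15-16%.

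A different setup gives the same pattern. With one mediator shifted 0.29 SD and a true share of 50%, the share ranges from 0.23 to 1.09 at 5 mm Hg (3.6% outside 0-1) and from −1.74 to 3.82 at 2.7 mm Hg (20% outside). The indirect effect ranges from 1.02 to 4.07 and from 0.50 to 2.37 mm Hg respectively.

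**4. Ability to show mediation.** In 100 simulated trials with percentile bootstrap intervals (not the planned BCa), the interval excluded zero as follows:
- at 2.7 mm Hg: 89% for the indirect effect, 33% for the proportion;
- at 5 mm Hg: 99% for the indirect effect, 84% for the proportion.

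**5. Overlap if mediators are fitted singly.** For k equally contributing mediators with common correlation r, the single-model shares sum in expectation to about joint share × (1 + (k − 1) × r).
- k = 2, r = 0.6, joint share 0.40: 0.40 × 1.6 = 0.64. Simulated medians are 59-63%.
- k = 6, r = 0.3, joint share 0.60: 0.60 × 2.5 = 1.5.
- k = 6, r = 0.5, joint share 0.60: 0.60 × 3.5 = 2.1.

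In one joint model with six mediators the shares sum to a median of about 0.60 at 5 mm Hg, so the double counting goes. The denominator problem stays: at 2.7 mm Hg even the joint sum is outside 0-1 in about 26% of trials.

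**The case against.** **The causal steps act as a gate.** The Baron and Kenny approach conventionally starts from a significant total effect, which would stop the trials that produce absurd ratios. Restricting the two-mediator simulation to trials with a significant benefit supports this. At 2.7 mm Hg the share then runs from 10% to 51%, with none outside 0-100%; at 5 mm Hg it runs from 19% to 71%. Two things limit the argument. The SAP does not state the gate, and the later methods it also cites can relax that step. Gating also has a price: at 2.7 mm Hg only about 40% of trials qualify, and their median share is about 26% against a true 40%, because only large denominators pass.

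**2.7 mm Hg is the unfavourable case.** It is the low end for videos alone; the SAP expects a stronger effect and powers for 5. This stands as far as it goes. A reader might infer that the proportion is uninterpretable at the design effect, and the calculations do not support that. The plan should nevertheless cope with a result the SAP itself reports having seen.

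**Nothing is hidden.** The numerator has to be computed anyway, and the planned intervals would reveal imprecision. True, but the SAP makes the ratio the stated result, and step 4 shows that the ratio is the weaker basis for judging H3.

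**Separate models are not stated.** A reader might infer from the wording that mediators are taken one at a time. The SAP says only that each receives a share, and a joint model remains open. The double counting is therefore conditional; the certain fault is that the choice is left unspecified.

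**Conclusion.** The point holds as a cheap improvement to a secondary analysis. The proportion mediated is the only H3 summary the SAP states. On the SAP's own inputs its denominator has a standard error of about 1.6 mm Hg. At 5 mm Hg the share is wide but mostly within 0-100%. Near 2.7 mm Hg it is unstable, with about 16% of estimates outside that range, while the joint indirect effect is well estimated. If correlated mediators are fitted singly, the shares cannot be added or ranked.

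The standard error rests on the SAP's figures and assumed 1:1 allocation. The mediator shifts, correlations and true shares are assumptions, so the percentages illustrate the behaviour and do not predict this trial's results. A reader might also infer that the trial's main conclusion is weakened. It is not: H1, its power and the Hypothesis 2 analyses are unaffected.

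**What to change.** Amend the SAP under Hypothesis 3, before outcome data are compared by arm:

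1. Make the indirect effect in mm Hg, with the planned 95% BCa bootstrap interval, the main H3 estimate. Take the joint indirect effect from one model containing the mediators measured in both arms.
2. Report any proportion as descriptive only, beside the mm Hg estimate and with its interval. Note that it is unreliable when the total-effect interval includes zero, and biased low if shown only when the total effect is significant.
3. Do not rank mediators by shares from single-mediator models.
4. Report emotional engagement with the stories separately, as a descriptive analysis within the intervention arm. Table 8 times the video transportation and homophily scales only after viewing, and the control procedure in Protocol 5.1 includes no viewing.

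The cost is SAP wording and a modest change to the mediation program, with no new data, visits or participants. There are two downsides. The headline becomes an effect in mm Hg instead of a percentage. And a parallel joint model still does not separate self-efficacy from behaviours it may act through, so the individual paths within the joint effect need cautious reading.
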